The feasibility study will be undertaken in two community hospitals in Sussex Community NHS Foundation Trust. The trust has 13 community hospitals (inpatient community units) located in West Sussex and East Sussex with approximately 300 inpatient beds. The study is undertaken in West Sussex. This is the locality with the highest proportion of people aged 85 years and over, with the highest corresponding provision of community hospitals. The two hospitals participated in the development workstreams involving consultations with staff and patients. The hospitals will be purposively selected from the four community hospitals involved in the staff consultation workstream three. Purposive selection for the feasibility evaluation is based on the criteria:

- Large facilities to capture a breadth of patients
- Geographical catchment areas of mixed levels of deprivation and ethnicity
- Patients with comparatively high levels of dependency
- Engagement and participation in the preceding development workstream

Study procedures

Selection and withdrawal of patient participants

Eligibility criteria for patients

- An inpatient in the community hospital for 24 hours or more during the study period.
- Aged 65 years or over
- Mental capacity to give informed consent, or for adults lacking capacity availability of an individual who knows them well to complete the research questionnaires

Selection of patient participants

The direct care team will identify potentially eligible patients and approach those meeting eligibility criteria, or for adults lacking capacity approach the nearest caregiver, family member or close friend to act as the personal consultee and/or complete the research questionnaires. The direct care team comprises the clinical teams and/or the clinical research nurses. They will provide patients/consultees with the respective information sheet or post/email to consultees as appropriate. Consultees will receive a follow-up invitation by telephone and/or email. Patients/consultees can decline or indicate interest in participating/advising participation by informing a member of the direct care team. Consultees may also reply via email, telephone or return the reply slip in the Freepost envelope. If no personal consultee is identified, or does not

respond to requests for advice, a nominated consultee will be asked to advise about the person's participation (or not).

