Feasibility of the research methods

Sample size

The patient total sample size is 40 patients across the two community hospitals, with sample 1 comprising 20 patients and sample 2 comprising 20 patients. We will review the recruitment rate for sample 1, if recruitment is feasible within the timeframe, we will increase the sample 2 size to n=30. The sample size is informed by understanding that feasibility studies should include a minimum of 30 patients, and account for attrition. Attrition is calculated at ~30% as a typical rate for a study in palliative care.⁴⁷ A sample of 40 is considered sufficient for a feasibility study to explore the feasibility of recruitment to the study and the parameters to inform the sample size calculation in a future pilot trial.⁶³ We will recruit a maximum of 12 patients lacking capacity to assess the feasibility of the consultee process to advise on participation, and proxy reporting of research data. Patients lacking capacity will be recruited in sample 1 (pre-SPACE) and sample 2 (after-SPACE embedded). We will review our consultee process in the sample 1 recruitment to identify potential modifiers to enable participation.

Main candidate outcome

We will explore the feasibility and acceptability of a proposed candidate main outcome comprising 'Patient/family anxiety and communication subscale' of the Integrated Palliative Outcome Scale (I-POS)⁶⁴⁻⁶⁶ ⁶⁷ ⁴⁹. Anxiety and communication are common distressing concerns for patients on admission to hospital and their families. These concerns are often exacerbated when clinical presentation is uncertain. The Patient/Family anxiety and communication subscale comprises 7 items of the I-POS⁶⁶. The items concern information, practical matters, shared feelings, at peace, patient anxiety, family anxiety, and patient depression. Items are scored from 0 (best) to 4 (worst) and can be completed by the patient or a proxy (e.g. staff or family member) for adults lacking capacity. The I-POS is the latest refinement and improvement of the well validated and widely used Palliative care Outcome Scale (POS) developed and tested in palliative care⁶⁶. The POS has been used in community and hospital settings, including in nursing homes (UK and the Netherlands), and in many different conditions including dementia,⁶⁷ heart failure⁶⁸, COPD,⁶⁹ cancer, neurological conditions,⁷⁰ and multiple comorbidity⁶⁷.

Secondary candidate outcomes

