- 1. Descriptive analysis on the number of patients screened for eligibility and the proportion of eligible patients recruited and reasons for decline, and differences between participants and non-participants e.g. age, gender
- 2. Descriptive analysis on completion of the SPACE documents from the patient record data extraction on when completed, proportion of missing data, and use over time e.g. IPOS-Dem to review and evaluate outcomes of care.
- 3. Examining the candidate main outcome of *patient/family anxiety and communication subscale* and secondary outcomes. We will examine missing data and evaluate the impact on results. We will explore the before (sample 1) and after (sample 2) measures and degree of change in the candidate main and secondary outcomes using non-parametric test for categorical data (e.g. Chi-Square) or parametric tests for continuous variables (e.g. T-Test).
- 4. Examine reasonable mean and variance estimates of the main outcome to inform the sample size calculation in a future pilot/full trial and estimates of inter-correlation co-efficient by examining variation between hospitals e.g. age, length of stay.
- 5. The data analysis in the economic evaluation will explore procedures to inform the economic evaluation in a pilot/full RCT. Economic evaluation is an emergent area in studies with patients with advanced progressive conditions and uncertainty surrounds best practice ⁷⁶.

Qualitative analysis

We will undertake a full coding of focus group and interview transcripts, non-participant observations and fieldnotes to identify themes using constant comparative approach⁹⁴ in NViVo⁹⁵. Data analysis will explore the range of experiences of staff using the documents in clinical care exploring feasibility and acceptability, solutions and barriers to enhance use, and potential benefit for patients and families. Quality appraisal will use procedures to ensure systematic attention to analysis and reporting e.g. analysis review meetings.

Ethics and regulatory approvals

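### Two purposively selected hospitals cannot give an intra-cluster correlation precise enough to plan a later trial, and item 4 of the quantitative analysis names age and length of stay, not the main outcome, as its examples

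*Protocol*

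**What the plan says.** Protocol, Data analysis, Quantitative analysis, item 4 has two parts. The first is to obtain mean and variance estimates of the main outcome for the sample size of a later pilot or full trial. The second, joined to it by 'and', is "estimates of inter-correlation co-efficient by examining variation between hospitals e.g. age, length of stay". The coefficient is not defined further. In a phrase about variation between hospitals it is most naturally the intra-cluster correlation, and I read it so.

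Under Study setting: "The feasibility study will be undertaken in two community hospitals in Sussex Community NHS Foundation Trust". On their choice: "The hospitals will be purposively selected from the four community hospitals involved in the staff consultation workstream three". The listed criteria include "Patients with comparatively high levels of dependency", along with large size to capture a breadth of patients, catchments of mixed deprivation and ethnicity, and engagement in the earlier work.

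The Sample size section fixes the numbers as follows: "The patient total sample size is 40 patients across the two community hospitals, with sample 1 comprising 20 patients and sample 2 comprising 20 patients". If recruitment goes well, "we will increase the sample 2 size to n=30". The stated basis is that "feasibility studies should include a minimum of 30 patients, and account for attrition", and on expected losses the section adds: "Attrition is calculated at ~30% as a typical rate for a study in palliative care".

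The main candidate outcome is the seven-item patient/family anxiety and communication subscale of the I-POS. Length of stay is listed as a process outcome. No ICC value, precision target or external source for an ICC is given.

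**The concern.** An ICC is the share of total variance that lies between clusters, so its precision depends mainly on the number of clusters. With two hospitals that component rests on a single contrast, and recruiting more patients in each does not change this. Purposive selection adds to the problem, because the two hospitals are not a random draw from the hospitals a later trial would use. Table 3 also has hospital 2 start with a process refined in hospital 1, so a difference between them would mix hospital with calendar time and stage of implementation.

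The second problem is the variable. A sample size formula for a clustered design needs the ICC of the outcome being compared. Variation in age describes case mix and variation in length of stay describes process. Neither stands in for the ICC of the I-POS subscale.

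What is at stake is the next trial, not this one. A value near zero by chance would suggest that clustering can be ignored, and a high value by chance would suggest the opposite.

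**Working it through.** **Inputs from the protocol.** Two hospitals; 40 patients, or 50 if sample 2 rises to 30; attrition about 30%.

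**The plan's own figure.** The protocol states no ICC to reproduce. The only design figure is the total of 40. Adding 30% to the minimum of 30 gives 30 × 1.3 = 39, close to 40. Dividing by the retained fraction gives 30 / 0.7 = 42.9, so 43. After 30% attrition, 40 × 0.7 = 28 remain. The ICC result does not depend on which route was used.

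**Assumptions.** An even split between hospitals, so m = 14 (28/2), 20 (40/2) or 25 (50/2) per hospital; approximately normal scores; both samples pooled within hospital; true ICC values of 0.01, 0.05 and 0.10 for illustration.

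**Formulas.** One-way analysis of variance with k = 2 hospitals:
- F = between-hospital mean square / within-hospital mean square, on 1 and 2(m − 1) degrees of freedom.
- ICC estimate = (F − 1) / (F + m − 1).
- 95% limits: divide F by the 97.5% and 2.5% points of the F distribution, then apply the same transformation.
- P(estimate ≤ 0) = P(F distribution ≤ 1/θ), where θ = (1 + (m − 1)·ICC) / (1 − ICC).

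**Worked case, m = 20, estimate 0.05.**
- F = (1 + 19 × 0.05) / 0.95 = 1.95 / 0.95 = 2.053.
- The F(1, 38) points are 5.446 and 0.000995.
- Lower: 2.053 / 5.446 = 0.377, giving (0.377 − 1) / (0.377 + 19) = −0.03.
- Upper: 2.053 / 0.000995 ≈ 2063, giving 2062 / 2082 = 0.99.
- P(estimate ≤ 0 when the true ICC is 0.05) = P(F(1, 38) ≤ 1/2.053 = 0.487) = 0.51.

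**Results.**

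| Patients per hospital | 95% CI for an estimate of 0.05 | P(estimate ≤ 0), true ICC 0.05 | Central 95% of estimates, true ICC 0.05 |
|---|---|---|---|
| 14 | −0.05 to 0.99 | 0.55 | −0.08 to 0.39 |
| 20 | −0.03 to 0.99 | 0.51 | −0.05 to 0.34 |
| 25 | −0.02 to 0.99 | 0.49 | −0.04 to 0.31 |

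With a true ICC of 0.05 the estimate would also exceed 0.10 in 24% of studies at m = 14 and 22% at m = 20. The assumed ICC does not change the picture: at m = 20, P(estimate ≤ 0) is 0.63 for a true ICC of 0.01 and 0.42 for 0.10.

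**The limit is the number of hospitals.** With 20 patients per hospital and an estimate of 0.05, the 95% interval is −0.02 to 0.58 with 4 hospitals, 0.00 to 0.19 with 13, and 0.01 to 0.12 with 30.

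**Consequence if the next trial is clustered by hospital.** Design effect = 1 + (n − 1)·ICC. With an assumed n = 20 per hospital it is 1.0 at ICC 0, 1 + 19 × 0.10 = 2.9 at ICC 0.10, and 1 + 19 × 0.99 = 19.8 at the upper limit. The interval therefore covers nearly the whole possible range of 1 to 20.

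**The case against.** Several points on the other side are fair, and they limit what can be claimed.

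- A reader might infer that the protocol will compute the ICC from age and length of stay and not from the outcome. The text does not go that far. The two variables are introduced as examples, in an item that opens with the main outcome, so an I-POS ICC is not excluded. What stands is that the item names other variables and does not name the outcome.
- A reader might infer that the next trial's sample size is certain to be wrong by a factor of about three. The protocol does not say that trial will be cluster-randomised; it speaks of a pilot and definitive trial, or a pilot/full RCT. The swing from 1.0 to 2.9 needs a hospital-clustered design, 20 patients per hospital and use of the bare point estimate. A pilot is also planned before any definitive trial. In addition, the clause about informing sample size attaches grammatically to the mean and variance; the link to the coefficient is natural but not spelled out.
- A reader might infer that the hospitals were chosen only to be alike. Two of the criteria seek a breadth of patients and mixed deprivation and ethnicity. Selection is still purposive, so the two hospitals are not a random sample.
- None of the four objectives mentions an ICC, and the analysis is said to focus on recruitment, missing data and use of the documents. That lowers the severity.

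None of this restores the estimate. Two hospitals leave one degree of freedom whichever variable is used.

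**Conclusion.** The concern holds, at moderate severity. Item 4 commits the study to a quantity that its design cannot estimate usefully. With two hospitals, a 95% interval from just below 0 to 0.99 leaves almost every value possible, and about half of such studies would give zero or less if the true ICC were 0.05. This rests on an even split, a one-way variance model and assumed true ICC values; the conclusion is the same from 0.01 to 0.10 and from 14 to 25 patients per hospital. Naming the I-POS subscale would correct the choice of variable but not the imprecision.

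Harm to a later trial is conditional on that trial being clustered by hospital and on the estimate being used as it stands. This study's own aims on recruitment, acceptability and missing data are unaffected, and nothing here shows the planned mean and variance estimates to be wrong.

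**What to change.** In item 4, remove the ICC as an input to sample size. Show main-outcome means by hospital descriptively. If an ICC is reported at all, make it that of the I-POS subscale, give its confidence interval and label it descriptive only. State that a planning ICC, if the next design needs one, will come from external multi-site data, with the sample size shown over a sensitivity range. It would also help to replace the undefined term with 'intra-cluster correlation' if that is what is meant.

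The cost is one sentence in the analysis section. It needs no extra data, patients or hospitals.
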